the capsule by irrigation in addition to the manipulation of intracapsular structures (3,4). It has been established that multimodal analgesia yields best pain control as different pain pathways are targeted with different drugs and techniques with regional anesthesia being one of the most prominent modalities (5). For a long time interscalene block (ISB) has been used for shoulder scope surgeries. Although it is an effective block, the procedure is not devoid of complications which include phrenic nerve affection and diaphragmatic paralysis which could affect respiration. Also, dural spread and brachial plexus injury are among the recorded complications (6,7). Even when these complications do not occur, interscalene block affects motor power of the arm while PENG block spares motor power affection which is a key factor regarding that shoulder scopes are usually day case surgeries.

Interscalene block produces an intense motor block of the upper limb muscles which may extend to the hand muscles leading to the discomfort of patients and predisposing them to injuries (8), patients are always advised to carry the numb limb in an immobilizer and to protect it till complete sensory and motor function returns.

Therefore, alternatives for interscalene block as suprascapular nerve blocks or supraclavicular nerve blocks are being researched. Pericapsular nerve group (PENG) block is one of the novel techniques that are being studied currently, its main advantage over interscalene is that the target is the peripheral nerve endings around the joint capsule rather than tackling large nerves as the brachial plexus trunks (9). It has been first introduced in hip arthroplasty and other hip surgeries and showed promising results; thus, it is being applied to shoulder scope surgeries (10).

Papers have been published investigating the efficacy of PENG block in hip surgery with different control and comparison groups, as was done by Mosaffa F et al when comparing PENG with fascia iliaca compartment block (11). Other studies were done on PENG block efficacy in shoulder surgery, but with comparison against suprascapular nerve block, and with the main focus on postoperative pain relief as a primary outcome rather than recovery of motor power. To our knowledge, this is the first study to compare between the effect of PENG block and interscalene block on muscle power of the hand in shoulder arthroscopic surgery.

Aim of the work

The aim of the study is to compare the effect of PENG block and interscalene block on the motor power of the hand and time to full recovery of motor affection if any.

Objectives:

- To assess effectiveness of PENG block in recovery of hand motor power compared with ISB
- To compare between PENG and ISB in controlling postoperative pain
- To assess effectiveness of PENG block in reducing postoperative opioid consumption compared with ISB

Hypothesis

We hypothesize that PENG block will be superior to interscalene nerve block regarding motor power sparing.

Ethical Considerations

This study will be conducted after taking approval of the research ethical committee. Written informed consent will be obtained from study participants or their legally authorized representative.

Methodology

I. Study design

Randomised comparative single blinded superiority study.

II. Study setting and location

This study will be conducted at the theatre for orthopedic surgeries at The Cairo University Teaching Hospital.

III. Study population

Patients scheduled for arthroscopic shoulder surgery

IV. Eligibility Criteria

1. Inclusion criteria

- Adult patients (age 22-60) scheduled for arthroscopic shoulder surgery under general anesthesia
- Both genders
- ASA grade I-II
- BMI less than 35
- Duration of surgery 90-120 minutes

2. Exclusion criteria

- ASA grade III-IV
- Allergy to local anesthetics
- Coagulation disorder (INR >1.2, Platelets <100,000), or recent intake of clopidogrel or warfarin within 1 week.
- Active infection at site of injection

V. Study Procedures

1. Randomisation

This is a single centre randomised comparative trial. Patients undergoing arthroscopic shoulder surgery will be randomised to receive either PENG block, which is the intervention group, or to receive interscalene block.

Randomisation will be done via computer generated random numbers which will be enclosed in envelopes with 60 envelopes in total, 30 for each group. This is a single blinded study so an anesthesiologist who will not partake in this study will open the envelopes and proceed with the allocated block. After the procedure, the anesthesiologist who will assess motor power recovery and collect postoperative data will also be blinded to the type of block given. Therefore, to reduce bias only the anesthesiologist and main researchers will be aware of the allocation, while the outcome data collector will be blinded.

2. Study Protocol

Patients in this study will be randomly assigned to one of two groups; Group A will receive PENG block and Group B will receive interscalene block. All patients will be evaluated preoperatively by routine lab investigations (full blood picture, serum electrolytes, liver and kidney function tests and coagulation profile).

Patients will be educated concerning the nature of the procedure and its possible complications, and all patients will sign a written informed consent. Short term fasting will be encouraged (6 hours for solid food, 2 hours for clear fluids). A 3rd generation cephalosporin will be given 30 min prior to the procedure as prophylaxis. Before admittance to the operation

theatre, a 22G cannula will be inserted and anxiolysis will be achieved by giving the patients midazolam 2 mg IV.

Upon arrival to the operation room, all patients will receive standard monitoring (Pulse oximeter, ECG, NIBP, Capnography), and baseline hemodynamic measurements of heart rate, systolic blood pressure (SBP), diastolic blood pressure (DBP) and mean arterial blood pressure (MAP) will be recorded. Also baseline muscle power of the hand on the same side of surgery will be measured using a digital dynamometer (Handeful Digital Hand Dynamometer, Handeful, CA, United States). The dynamometer we are using is a digital one that measures grip strength in kilograms.

Group P (PENG Block group):

Patients in this group will receive PENG block prior to induction of general anesthesia. Patient will be placed in supine position with arm abducted and externally rotated. Skin will be disinfected then under ultrasonic guidance (ACUSON X300™ ultrasound system, Siemens Medical Solutions, Inc, Germany) a high frequency linear ultrasound probe (12MHz) will be applied longitudinally between the head of humerus and coracoid process then local infiltration will be done using 29 G needle to apply 3 mL lidocaine 2%. After identification of deltoid muscle and subscapularis muscle tendon which should be immediately superficial to humeral head, a 22-gauge needle (SonoPlex® STIM, PAJUNK® Medical System L.P., Germany) will be advanced to pierce the deltoid and target the tip to be just touching the subscapularis tendon. A test dose of 3 ml saline solution will be injected to visualise the separation of deltoid from subscapularis and confirm and the

needle is in the correct position. Afterwards 15 ml of 0.25% bupivacaine will be injected to complete the block. A wait time of 30 minutes will be allowed before induction of general anesthesia to ensure the full activation of the block.

Group I (Interscalene block):

Patients in this group will also receive ISB prior to general anesthesia. With patient placed in supine position and head facing away from the side being blocked, the skin is disinfected first then the linear ultrasound probe is placed transversely on the neck to identify the carotid artery. Then the transducer is moved slightly laterally until middle and anterior scalene muscles are identified with the brachial plexus between them then local infiltration will be done using 29 G needle to apply 3 mL lidocaine 2%. A 22-gauge needle will be introduced in plane in a lateral-medial direction aiming towards the space between the roots. After a 3 ml saline injection for confirmation of proper position, 15 ml of 0.25% bupivacaine will be injected with advancement of the needle as the roots are displaced by the injectate. Adequate injection will be confirmed by visualizing the roots being surrounded by the local anesthesia infiltrate.

Patients receiving either block will wait 30 minutes before induction of general anesthesia. Interscalene block will be tested using pin prick test on shoulder and upper arm area, by loss of shoulder abduction, and finally by passively moving the arm to check for loss of previously present pain on movement. PENG block will be tested using pin prick test and loss of pain on passive movement as well. A block not fulfilling these examinations will be

deemed unsuccessful, and the patients will be given additional opioids in the form of morphine 5 mg IV with induction of general anesthesia. These patients will be excluded from the study. Before induction of general anesthesia another dynamometer measurement will be recorded.

In both groups patients will receive general anaesthesia using the standard centre preferences; IV induction via propofol 2 mg/kg and fentanyl 1 mic/kg for induction, then atracurium 0.5 mg/kg for intubation followed by 0.1 mg/kg every 20 minutes for maintenance. An additional dose of fentanyl 1 mic/kg will be administered on skin incision.

For maintenance of anaesthesia, isoflurane will be administered at a concentration of 1.2-2%, and the patient will be mechanically ventilated using parameters that will achieve normal end-tidal CO₂ (35-45 mmHg) and oxygen saturation (> 95%). To maintain relaxation atracurium will be given as 0.1 mg/kg every 20 minutes.

Intraoperative hemodynamics will be measured at 10 min intervals, both heart rate and blood pressure values (SBP, DBP and MAP) will be recorded. Bradycardia defined as heart rate below 60 beats per minute, and bradycardia will be managed if heart rate drops below 55 bpm by giving atropine 0.04 mg/kg IV bolus to be repeated after 5 minutes if needed. Hypotension also described as SBP below 90 mmHg will be managed by giving ephedrine 5-10 mg IV bolus.

At the end of surgery, patients will be given 1 g acetaminophen IV, and NSAID will be given in the recovery room in the form of ketorolac 30 mg IV.

For recovery, neuromuscular blockade will be reversed using neostigmine 0.04 mg/kg and atropine 0.02 mg/kg, and the patient will be extubated fully awake and when adequately reversed which is clinically assessed as the patient achieves tidal volumes > 5ml/kg.

Patients will be transferred to the post anesthesia care unit (PACU), and same intraoperative hemodynamics will be measured every 10 min through their PACU stay duration. With regards to postoperative management, Visual analog scale (VAS), which is a scale from 0 to 10 where 0 represents no pain at all and 10 represents the most severe pain, will be used to assess pain. VAS assessment will be carried out during the 1st hour at the PACU then at 2, 4, 6, 12, and 24 hours postoperative during day 1, and If VAS is >4, opioids will be administered in the form nalbuphine 5mg IV, and the time to first dose and total number of doses given will be noted not to exceed 60 mg per day. Also, hand grip power will be assessed at the PACU then at 2, 4, 6, 12, and 24 hours postoperatively, and this will be done using the digital dynamometer. The readings will be compared with a measurement of the patient's baseline grip power of the same hand taken before surgery and with readings taken after block administration.

3. Measurement tools

- Hand grip power will be measured using digital dynamometer at these intervals: immediately postoperative at PACU and then at 2, 4, 6, 12, and 24 hours postoperative, and results compared with baseline measurement.
- Time for full recovery of hand grip power.

- Intraoperative hemodynamics in the form of heart rate and mean blood pressure every 10 minutes.
- Postoperative pain will be measured using VAS score at these intervals: immediately postoperative at PACU and then at 2, 4, 6, 12, and 24 hours postoperative.
- Postoperative hemodynamics in the form of heart rate and mean blood pressure in PACU every 10 minutes until discharge
- Time to first opioid dose
- Total amount of opioid administered.
- Patient satisfaction will be measured at 24 hours postoperative using self reported satisfaction scale (1= very dissatisfied and 5=very satisfied)

VI. Study outcomes

1. Primary outcome

- Time for full recovery of hand power, defined as time from start of block activation till time of achieving grip strength similar to patient's baseline

2. Secondary outcome(s)

- Hand grip power after surgery at PACU, then at 2, 4, 6, 12, and 24 hours.
- Time to first analgesia request
- VAS score after surgery at rest and during movement at PACU then at 2, 4, 6, 12, and 24 hours

- Patient satisfaction score at 24 hours postoperative
- Intraoperative hemodynamics

Statistical Analysis

I. Sample size

Based on a previous study (12) the duration of motor block in patients receiving ISB was 711 ± 151 min (REF). A minimum sample of 50 patients is needed to detect a 20% reduction in duration of motor block. The study power was set at 90% and alpha error was set at 0.05. Sample size was calculated using the MedCalc Software V14. The number of envelopes will be increased to 60 (30 in each group) to compensate for dropouts.

II. Statistical analysis

Statistical package for social science (SPSS) software, version 26 for Microsoft Windows (SPSS inc., Chicago, IL, USA) will be used for data analysis. Categorical data will be presented as frequency (%) and will be analyzed by the chi square test. Continuous data will be checked for normality using the Shapiro-Wilk test and will be presented as mean (standard deviation) or median (interquartile range) as appropriate. Continuous data will be analyzed using unpaired the t test or the Mann Whitney test according to normality of the data. Repeated measures will be analyzed using the analysis of variance (ANOVA) for repeated measures with post-hoc pairwise comparisons using the Bonferroni tests. A P-value less than 0.05 will be considered statistically significant.

References

- (1) Farmer KW and Wright TW. Shoulder arthroscopy: the basics. *J Hand Surg Am.* 2015 Apr; 40(4):817-21.

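### The main researchers know the allocation by rule, so exclusions after randomisation and analysis choices can be influenced with the arm known

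*Combined protocol and SAP*

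**What the plan says.** V. Study Procedures, 1. Randomisation, sets three rules.

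- **The set.** Allocation uses "computer generated random numbers which will be enclosed in envelopes with 60 envelopes in total, 30 for each group". No blocks or strata are described.
- **The opener.** "an anesthesiologist who will not partake in this study will open the envelopes and proceed with the allocated block".
- **Who knows.** "to reduce bias only the anesthesiologist and main researchers will be aware of the allocation", "while the outcome data collector will be blinded".

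V.2 Study Protocol, under Group I, then describes how each block is tested before induction. For one arm: "Interscalene block will be tested using pin prick test on shoulder and upper arm area, by loss of shoulder abduction", and then by loss of pain on passive movement. For the other: "PENG block will be tested using pin prick test and loss of pain on passive movement as well". Of patients whose block fails these tests it says: "These patients will be excluded from the study". It does not say who judges failure.

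Statistical Analysis, II, gives a rule for choosing between the t test and the Mann-Whitney test. It names no masked analyst and defines no analysis set. The Hypothesis section commits the researchers to expecting superiority of the PENG block for motor sparing.

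**The concern.** The researchers' knowledge of the arm is a stated rule, not a gap in the description, and the protocol presents it as a measure against bias. Yet the step that does require knowledge of the arm, giving the block, is assigned to someone outside the study.

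Blinding the person who reads the dynamometer protects the reading. It does not protect decisions about which randomised patients stay in the comparison or how their data are analysed. If those decisions lean towards the hypothesis, the estimated difference in recovery time can be biased even though every grip reading was taken blind.

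A second, conditional risk concerns enrolment. Anyone who knows the past allocations in a fixed 30:30 set can count what remains. If that person also decides whom to enrol and when, the arms may differ at entry.

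**Working it through.** **1. Who needs to know the arm.**

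- Opening the envelope and giving the block: the outside anaesthesiologist, who must know.
- Measuring outcomes: the data collector, who is blinded.
- Main researchers: they know the arm, and no task that requires it is assigned to them.
- Recruiting, and testing the block: no person is named.

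**2. Exclusions.** Failed blocks are removed after randomisation. Loss of shoulder abduction is part of the test in the interscalene arm only, so whoever applies the tests must know the arm. This is a motor criterion in a trial whose primary outcome is motor recovery. Nothing requires the decision to be documented before outcomes are known or kept independent of the researchers. No analysis of all randomised patients is planned as a check.

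**3. Analysis.** The choice of test follows a normality check. Other choices are open: there is no analysis set, and the primary outcome defines recovery as a return to about baseline grip without a numerical threshold. Nothing requires these to be settled with the arms masked.

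**4. The plan's own figures.** From Statistical Analysis, I: mean 711 min, SD 151 min, 20% reduction, power 90%, alpha 0.05 (taken as two-sided).

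- Difference: 0.20 × 711 = 142.2 min.
- Normal approximation: 2 × (1.960 + 1.282)² × 151² / 142.2² = 23.7, so 24 per arm, 48 in total.
- Two-sample t test: 24.7, so 25 per arm. This gives the stated 50.
- Allowance for dropouts: 60 − 50 = 10 patients, or 10/60 = 16.7%. The plan does not say whether excluded failed blocks count against these ten.

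The sample size is sound and is not part of this point.

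**5. Guessing advantage, if past allocations are known.** Assume a random ordering of 30 and 30, and a guesser who always names the arm with more envelopes left.

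- Expected correct guesses: n + (4ⁿ / C(2n, n) − 1)/2 with n = 30. Here 4³⁰ / C(60, 30) = 9.749, so 30 + 8.749/2 = 34.37 of 60, or 57.3% against 50% by chance.
- Expected number of final allocations that are certain: 2n/(n + 1) = 60/31 = 1.94.
- With k envelopes already opened, the chance that the next guess is right is the sum over i of [C(30, i) C(30, k − i) / C(60, k)] × max(30 − i, 30 − k + i)/(60 − k). This gives 50% at patient 1, 55% at patient 31, 61% at patient 50, 75% at patient 59 and 100% at patient 60.
- Averages: 54.7% over patients 1 to 50 and 70.2% over patients 51 to 60. Check: 50 × 0.547 + 10 × 0.702 = 34.4.
- The same formula within blocks of 4 gives 2.83/4 = 70.8%, and within blocks of 6 gives 4.1/6 = 68.3%. Small blocks would be easier to guess, so changing the scheme is not the remedy.

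**The case against.** A reader might infer that upcoming allocations can be predicted and that enrolment will be steered. The documents do not support this. They do not say that the main researchers recruit, whether they learn an allocation before or after it is made, or that they hold the list. For most of the trial the advantage is small, and an unblocked set of 60 is harder to guess than the usual small blocks. Nor can the guessing advantage be turned into minutes of bias or an inflated error rate: that needs an assumed size of steering, and the documents name no baseline feature from which recovery time could be foreseen. This objection stands, and the enrolment risk is stated only as conditional and modest.

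The trial is also openly single blinded, its outcome is an instrument reading taken by a blinded assessor, and the choice of test follows a rule. These features limit the room for bias, but they do not cover exclusions, the analysis set or the recovery threshold.

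A further objection is that masking the main researchers would not mask the exclusion decision, because the block tests themselves reveal the arm. If a main researcher performs those tests, that person cannot be masked at all. This is correct. It means that masking alone is not enough and that the plan must say who tests the block.

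**Conclusion.** The concern holds in a limited form. The protocol makes the main researchers aware of the allocation without a stated need, and blinds by name only the outcome data collector. That leaves exclusions after randomisation and analysis choices open to influence with the arm known. This follows from the text and needs no numerical assumption; the size of any resulting bias cannot be derived from the documents.

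The enrolment risk rests on two assumptions that the documents neither state nor rule out: that the researchers recruit, and that they know all past allocations. Under both, they would guess 57% of allocations correctly overall and about 70% in the last ten, with about 2 of 60 certain.

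This is a cheap improvement that should be made. It does not show that the design is invalid or that steering will occur.

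**What to change.** **Knowledge of the arm (V.1).** Reword the sentence so that only the anaesthesiologist who opens the envelope and gives the block knows the allocation, and state that this person takes no part in recruitment, outcome assessment or analysis. Open each envelope only after the patient has consented and been entered in the log. Keep the main researchers unaware of the allocation until the data set, including all exclusions, is locked. Run the primary analysis with the arms coded.

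**Exclusions (V.2 and Statistical Analysis, II).**

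- Name who tests the block. That person cannot be masked, so have each failure and its reason recorded before any outcome is measured.
- Keep the reasons from the masked researchers until lock, because a failed abduction test identifies the arm.
- Continue collecting outcomes on these patients.
- Report exclusions by coded arm, and add an analysis of all randomised patients beside the planned one.

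**Cost.** This is mostly protocol wording. The independent anaesthesiologist is already in the plan and the sample size does not change. The added work is a short failure record and continued follow-up of patients with failed blocks. The independent anaesthesiologist must also hold the allocation record and be reachable if care requires the block type. If a main researcher was to test the blocks, that task would have to pass to someone else.

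### No pain score is recorded before the block, so the pain item of the block test that decides exclusion has no reference and the VAS analysis has no baseline covariate

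*Combined protocol and SAP*

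**What the plan says.** Study Protocol (V.2) lists what is taken on arrival in theatre, before either block: "baseline hemodynamic measurements of heart rate, systolic blood pressure (SBP), diastolic blood pressure (DBP) and mean arterial blood pressure (MAP) will be recorded". It continues: "Also baseline muscle power of the hand on the same side of surgery will be measured using a digital dynamometer". Pain is not on the list. After the 30-minute wait, the block is tested and "Before induction of general anesthesia another dynamometer measurement will be recorded"; again no pain score is mentioned.

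The block test appears at the end of the Group I text in V.2 and differs by arm. For interscalene block it has three items: pin prick, loss of shoulder abduction, and "passively moving the arm to check for loss of previously present pain on movement". For the other arm, "PENG block will be tested using pin prick test and loss of pain on passive movement as well". The reference to earlier pain stands only in the interscalene sentence. On failure the text begins "A block not fulfilling these examinations will be" and goes on to class the block as unsuccessful. It provides for additional opioid at induction and then says: "These patients will be excluded from the study".

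Measurement tools (V.3) starts the VAS schedule after surgery: "Postoperative pain will be measured using VAS score at these intervals: immediately postoperative at PACU and then at" five later times up to 24 hours. Study outcomes (VI) lists VAS, at rest and on movement, as one of five secondary outcomes without ranking them. Eligibility Criteria (IV) contains nothing about pain. The Statistical analysis section names no covariate for any outcome.

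**The concern.** Loss of pain is a change, and a change needs a starting value. The plan makes this change part of a test that removes randomised patients, but does not record the starting value and does not require that there be pain to lose. Two testers could include and exclude the same kind of patient, each following the text, and the data could not settle who was right. The test differs by arm, so anyone applying it knows the allocation, which makes undocumented discretion over exclusions less comfortable.

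The second consequence is smaller. Comparing pain control is one of the three stated objectives. With 30 patients per group, a chance difference in preoperative pain could be neither shown in a baseline table nor adjusted for.

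A pre-block score cannot be recovered once the block has been given, so the decision has to be made before recruitment.

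**Working it through.** **1. Is pain scored anywhere before the block?** The measurement occasions in V.2 and V.3, set side by side:

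| Occasion | Recorded | Pain score |
|---|---|---|
| Arrival in theatre, before block | Heart rate, blood pressure, grip | None |
| After the 30-minute wait, before induction | Grip; block test applied | None |
| During surgery | Heart rate, blood pressure | None |
| PACU to 24 hours (six times) | Grip, VAS; haemodynamics in PACU | Yes |

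No pre-block pain score exists. The tester may learn informally whether the shoulder hurt, but the plan does not have this written down.

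**2. What does the test say for a patient with no prior pain on movement?** Such patients are eligible under section IV. Two readings are open:

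- Literal: pain must have been present and must have gone. The patient cannot show this, fails the item and is excluded.
- Loose: there must be no pain on passive movement now. The patient passes automatically, and the item says nothing about the block.

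The text does not choose between them.

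**3. How far could this reach the primary outcome?** Only through exclusions. The plan's own sample size comes first. Inputs from Sample size: mean 711 min, SD 151 min, 20% reduction, power 90%, alpha 0.05 (taken as two-sided, which the plan does not state).

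- Difference = 0.20 × 711 = 142.2 min; standardised, 142.2 / 151 = 0.94.
- Normal approximation, n per arm = 2 × (1.960 + 1.282)² × 151² / 142.2² = 23.7, so 24 per arm, 48 in total.
- Two-sample t test: 24.7, so 25 per arm, 50 in total. This matches the stated 50.
- Reserve: 60 − 50 = 10 patients, or 10 / 60 = 16.7%.

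The documents do not give the share of patients without pain on passive movement. Assuming 5% to 15%, 0.05 × 60 = 3 to 0.15 × 60 = 9 patients would be affected on the literal reading. Power of the t test (equal arms, losses unrelated to outcome):

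| Patients analysed | Lost | Power |
|---|---|---|
| 60 | 0 | 94.8% |
| 57 | 3 | 93.7% |
| 54 | 6 | 92.4% |
| 50 | 10 | 90.4% |
| 48 | 12 | 89.1% |

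Even 9 losses leave 51 patients, with power above 90%, if nothing else draws on the reserve.

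**4. What would a baseline VAS be worth?** Linear adjustment for a baseline with correlation r multiplies the residual variance at one time point by 1 − r². The documents give no r; 0.3 to 0.5 is assumed.

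- r = 0.3: 1 − 0.09 = 0.91, so 9% of the variance is removed; standard error × √0.91 = 0.954.
- r = 0.5: 1 − 0.25 = 0.75, so 25% is removed; standard error × √0.75 = 0.866.

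Confidence intervals for a VAS difference would be about 5% to 13% narrower.

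**The case against.** The strongest reply is that the block-test sentence is conditional in spirit: if moving the arm hurt before, check that it no longer does. A clinician would then pass a pain-free patient without hesitation. That reading is reasonable, so a reader who infers that pain-free patients cannot pass, and count as failures whatever the block did, goes further than the text. What stands is that the text does not settle the matter and no record would show how it was settled.

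Four other inferences are tempting and not supported:

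- *The reserve will be used up.* The pain-free share is an assumption, and even its upper value stays within the 10 spare patients. Genuine block failures and dropouts share that reserve, but the documents give no rate for them.
- *The VAS comparison is biased without a baseline.* Randomisation makes the unadjusted comparison of postoperative scores valid, and no adjustment was planned. The loss is precision and a check of balance.
- *VAS is a key outcome, so the gain can be expressed in patients.* The secondary outcomes are unranked. The 50 patients were calculated for motor block, and VAS has no power calculation to which a gain could be applied.
- *The exclusions will differ between arms.* The tester will know the arm and the tests differ, so this is possible. Nothing in the documents shows a direction or a size.

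It is also fair to say that a baseline score does not cure exclusion after randomisation, which is a separate matter, and that the variance formula describes linear adjustment at one time point. It does not carry over directly to the Mann-Whitney test, which the plan also allows.

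**Conclusion.** The point holds as a gap that is cheap to close, not as an error that invalidates an analysis. It is certain from the text that no pain score precedes the block, that the exclusion test relies on loss of pain, that eligibility does not require such pain, and that no rule covers patients without it. The test is undefined for them, and the plan lists no data from which its application could be checked.

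The effect on the primary outcome runs only through exclusions. At the assumed 5% to 15% pain-free share it would leave power above 90% if there were no other losses. The main harm is therefore uncontrolled exclusion rather than lost power. For VAS the gain from adjustment is about 9% to 25% of the variance at a given time point, resting wholly on the assumed correlation of 0.3 to 0.5.

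**What to change.** - **Study Protocol (V.2) and Measurement tools (V.3):** add VAS at rest and on a standard passive movement, taken just before the block beside the baseline grip reading and in the same way in both arms, preferably before the envelope is opened. Use the same passive movement in the block test, so that the test has a recorded reference.
- **Baseline table:** show both scores by arm, with the number of patients who had no pain on movement.
- **Statistical analysis (II):** use the matching pre-block score as a covariate in the VAS analyses, by ANCOVA at each time point or by a repeated-measures model that includes baseline.
- **Block-test wording (V.2):** the investigators must reconcile it with patients who have no recorded pain beforehand. Failing the test also changes the patient's analgesia, so this is a clinical decision, and no rule is proposed here.

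The cost is two scores at an assessment that already takes place, one case-report-form line and one covariate. No visit is added, and the sample size of 50 raised to 60 does not change.
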